7.4 Visit 1a: Baseline

The subjects should attend the first visit wearing their habitual lenses.

If they are not wearing their lenses, reschedule the visit.

The following procedures will be conducted on all subjects:

- i. Allow the subject to read the Participant Information Sheet and Informed Consent and explain the nature, purpose, risks of the study etc. If he/she is agreeable, ask the subject to sign the Informed Consent Form and initial where appropriate. The investigator (or person taking the consent) should also sign the consent form. Provide the subject with a copy and retain the original.
- ii. The subject is assigned with a Subject ID number according to the Enrolment Log. Subjects must be enrolled sequentially. Enter details on Enrolment Log as outlined on the form.

Baseline Measurements and Eligibility:

The following baseline measurements will be recorded on the Baseline eCRF:

- i. Subject demographics (age, sex, medications and associated medical history, allergies)
- ii. Habitual lens comfort (on insertion, during the day and prior to removal, 0-10)
- iii. Symptoms, problems and complaints
- iv. Vision
 - Subjective vision quality: distance (0-10 scale)
 - Monocular high contrast (HC) visual acuity (VA) with CLs (Snellen/logMAR to the nearest letter)
 - Spherical over-refraction (SOR)
 - Monocular and binocular HC DVA with SOR
- v. Wearing times – habitual lenses:
 - Wearing time at visit
 - Typical insertion time
 - Typical removal time
 - Typical time CL comfort deteriorates
 - Maximum wearing time in last month (hrs.)
 - Days worn per week
- vi. Details of habitual lenses and care system:
 - Lens brand
 - Care system brand

- vii. Rewetting drop usage (type and frequency),
- viii. Lens surface characteristics - habitual lenses
 - Lens surface wetting (0-4)
 - Lens deposits (film: 0-4; no. of white spots)
- ix. Lens fit - habitual lenses
 - Centration (0-2)
 - Corneal coverage (Y/N)
 - Post-blink movement (0-4)
 - Tightness on push-up (0-4)
 - Overall fit acceptance (0-4) and reason if Grade 2 or less.
- x. Remove habitual lenses
- xi. Full ocular health
- xii. Monocular spherocylindrical refraction and monocular HC distance VAs (logMAR or Snellen to the nearest letter)
- xiii. Biometry: Horizontal visible iris diameter (HVID), palpebral aperture (PA), keratometry (D/mm)
- xiv. Slit lamp examination
 - Limbal hyperemia (0-4)
 - Bulbar hyperemia (0-4)
 - Stromal edema (0-4)
 - Vascularization (0-4)

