 - Palpebral conjunctival hyperemia (0-4)
 - Upper palpebral roughness (0-4)
 - Corneal staining by sector (type 0-4)
 - Conjunctival fluorescein staining by quadrant (0-4)
 - Other findings (0-4)

See Appendix 4 for grading scales and measurement instructions.

- xv. Complete the eligibility checklist

If at this point the subject is found to be ineligible, then complete an Exit eCRF and exit the subject from the study.

If eligible, the subject will be assigned to one of the four lens types allocated to the site and assigned to one of the study solutions.

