7.5.2 Visit 2: 1-week Follow-up

The 1-week follow-up visit will be scheduled 1 week (7 days ± 3 days) from the lens dispensing date. The subject should wear the lenses 1 to 3 hours prior to the appointment. This has been shown to be the time period when solution-induced corneal staining is most evident.⁵ If the subject attends without lenses or with more than 3 hours of lens wear on that day and they are not having any problems with their lenses or the study solution, the visit should be rescheduled, if possible within the visit window.

The following clinical test variables will be recorded on the Follow-Up Visit eCRF:

- i. Wearing times:
 - Days worn since last visit
 - Typical insertion time
 - Typical removal time
 - Typical time CL comfort deteriorates
 - Maximum wearing time since last visit (hrs.)
 - Wearing time today (hrs.)
- ii. Rewetting drop usage (type and frequency)
- iii. Symptoms, problems and complaints
- iv. Subjective assessments
 - Overall comfort on insertion, during the day and prior to removal (0-10)
- v. Vision
 - Subjective vision quality: distance (0-10 scale).
 - Monocular VA (CL, Snellen/logMAR to the nearest letter)
 - Spherical over-refraction (SOR)
 - Monocular HC DVA with SOR
 - Binocular distance VA with CLs
- vi. Lens surface characteristics
 - Lens surface wetting (0-4)
 - Lens deposits (film: 0-4, no. of white spots)
- vii. Lens fit
 - Centration (0-2)
 - Corneal coverage (Y/N)
 - Post-blink movement (0-4)
 - Tightness on push-up (0-4)
 - Overall fit acceptance (0-4) and reason if Grade 2 or less
- viii. Remove lenses and store in sterile saline
- ix. Slit lamp examination
 - Limbal hyperemia (0-4)
 - Bulbar hyperemia (0-4)
 - Stromal edema (0-4)
 - Vascularization (0-4)
 - Palpebral conjunctival hyperemia (0-4)
 - Upper palpebral roughness (0-4)
 - Corneal staining (type 0-4)
 - Conjunctival fluorescein staining by quadrant (0-4)
 - Other findings (0-4)

See Appendix 4 for grading scales and measurement instructions.

Rinse away fluorescein with non-preserved saline.

Re-insert study lenses.

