10.2 Statistical Analysis Plan

General considerations: All data summaries and statistical analyses will be performed using the SAS software Version 9.4 or higher (SAS Institute, Cary, NC). Throughout the analysis of data, the results for each subject/eye will be used when available for summarization and statistical analysis. Missing data will be excluded from the analysis. Unscheduled visits will be excluded from the statistical analysis.

Descriptive statistics will be reported by solution type at baseline, dispensing, and each follow-up visit according to ISO 11980:2012. Continuous variables will be summarized using sample size (N), mean, standard deviation (SD), minimum and maximum, and categorical data variables will be summarized using the sample size, frequency distribution (count and percentage of subjects or eyes in each category), mean, median and SD.

Analysis Population: Statistical Analysis for hypothesis testing will be performed on all evaluable subjects. All inference will be carried out with an overall type I error rate controlled at 0.05.

Analysis of comfort: Results will be analyzed using a linear mixed model including the experimental design factors: solution type, visit and their interaction will be included as fixed effect factors and site and subject as random effects.

Comparisons between the test and control solutions will be carried out using pairwise one-sided confidence intervals constructed for least-square mean differences (mean difference calculated as Test minus Control). Non-inferiority will be concluded if the lower confidence limit is greater than -1.0.

Analysis of visual acuity: Results will be analyzed using a linear mixed model including the experimental design factors: solution type, visit and their interaction will be included as fixed effect factors and site and subject as random effects.

Comparisons between the test and control solutions will be carried out using pairwise one-sided confidence intervals constructed for least-square mean differences (mean difference calculated as Test minus Control). Non-inferiority will be concluded if the upper confidence limit is less than +0.05 logMAR.

Analysis of wettability: Results will be analyzed using a linear mixed model including the experimental design factors: solution type, visit and their interaction will be included as fixed effect factors and site and subject as random effects.

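### The seven primary mixed models omit the Visit 1a value of the endpoint, giving up precision that would need no new data

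*Combined protocol and SAP*

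**What the plan says.** Section 2.1 lists seven primary non-inferiority hypotheses. Four concern efficacy (comfort, logMAR visual acuity, wettability, deposits) and three concern safety (corneal staining, limbal hyperemia, bulbar hyperemia). Section 10.2 gives the same model for all of them: "Results will be analyzed using a linear mixed model including the experimental design factors: solution type, visit and their interaction" as fixed effects, plus random site and subject. The slit lamp model has the same terms, applied to sector averages. Neither a baseline covariate nor a change-from-baseline response is named. Baseline enters section 10.2 only through the descriptive summaries.

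Two general rules in section 10.2 also bear on the point: "Missing data will be excluded from the analysis", and "the results for each subject/eye will be used when available for summarization and statistical analysis".

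Section 7.4 records every one of the seven endpoints at Visit 1a. Examples are "Habitual lens comfort (on insertion, during the day and prior to removal, 0-10"), "Lens deposits (film: 0-4; no. of white spots") and "Corneal staining by sector (type 0-4"). Monocular visual acuity with lenses, surface wetting and both hyperemia grades are on the same list. Assignment comes only after these measurements and a passed eligibility checklist: "the subject will be assigned to one of the four lens types allocated to the site and assigned to one of the study solutions".

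**The concern.** A pre-randomization measurement of the endpoint is usually the natural covariate to consider for a follow-up comparison. Here it exists for all seven endpoints and goes unused in inference. For comfort, the follow-up item in section 7.5.2, "Overall comfort on insertion, during the day and prior to removal (0-10"), has the same three ratings as Visit 1a.

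Visit 1b could not do this job for every model. It has a single comfort rating after 10-15 minutes of settling, and section 7.5 lists no deposit grade there, although Table 3 ticks a combined wetting-and-deposits row. Visit 1a is therefore the one pre-solution visit that serves all seven.

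At stake is power. Section 10.1 bases the sample size on ISO 11980:2012 and gives no SD, power or expected difference, so the plan does not show that the seven tests have power to spare.

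A smaller gap sits in the same text. Section 10.2 does not say which visits are responses, or at which visit the Test minus Control difference is judged. If pre-solution visits were averaged into that difference, any true difference would shrink toward zero, which favours non-inferiority. The plan does not state that reading, and contrasts made visit by visit would be unaffected.

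**Working it through.** **The plan's own figure.** The Synopsis aims for 180 completers and section 10.1 assumes drop-out below 10%. 180/(1 − 0.10) = 200, and a 2:1 split gives 133 and 67, as stated. No power is stated, so none can be reproduced.

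**Inputs from the documents.** 120 test and 60 control completers (Synopsis: 20 and 10 in each of six lens groups). Margins of 1.0 for comfort, 0.05 logMAR for VA and 0.5 for each 0-4 grade (section 2.1). One-sided intervals and an overall type I error of 0.05 (section 10.2). The confidence level of each interval is not given; 0.05 is used below, with 0.025 as a check.

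**Assumed.** All SDs, the baseline-to-follow-up correlation r, the between-eye and between-visit correlations, and a true difference of 0.

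**Does the planned model already use baseline?** No. With a random subject intercept and complete data, entering Visit 1a as an ordinary visit level with a free solution-by-visit interaction leaves the variance of the month-1 difference unchanged (ratio 1.000 at r = 0.3, 0.5 and 0.7). Covariate adjustment multiplies that variance by 1 − r².

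| r | SE ratio √(1 − r²) | SE reduction |
|---|---|---|
| 0.2 | 0.980 | 2% |
| 0.3 | 0.954 | 5% |
| 0.5 | 0.866 | 13% |
| 0.7 | 0.714 | 29% |

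In terms of sample size, 180 adjusted completers are worth about 180/0.91 = 198, 180/0.75 = 240 and 180/0.51 = 353 unadjusted ones at r = 0.3, 0.5 and 0.7.

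**Power.** √(1/120 + 1/60) = 0.1581. Power = Φ(margin/(SD × 0.1581 × k) − 1.645), with k = √(1 − r²) for one value per subject. For comfort with SD 2.5:

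- r = 0: 1/(2.5 × 0.1581) = 2.530, and Φ(0.885) = 81.2%.
- r = 0.5: 2.530/0.866 = 2.921, and Φ(1.276) = 89.9%.

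| Endpoint, assumed SD | r = 0 | r = 0.2 | r = 0.5 |
|---|---|---|---|
| Comfort, 2.5 | 81.2% | 82.6% | 89.9% |
| Comfort, 2.0 | 94% | 94% | 98% |
| VA, 0.12 | 83.9% | 85.2% | 91.9% |
| VA, 0.10 | 94% | 94% | 98% |
| 0-4 grade, 1.0 | 93.5% | 94.3% | 97.8% |
| 0-4 grade, 0.8 | 99.0% | 99.2% | 99.8% |

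At one-sided 0.025, going from r = 0 to r = 0.5 moves comfort (SD 2.5) from 71.6% to 83.2% and VA (SD 0.12) from 75.0% to 86.1%.

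**More than one value per subject.** Starting power is then higher.

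- VA, SD 0.12, both eyes, between-eye correlation c: k = √((1 + c)/2 × (1 − r²)). For r = 0/0.2/0.5, c = 0.5 gives 91.9/92.8/96.9% and c = 0.7 gives 88.8/89.8/95.1%. A simulation with a random subject intercept and a per-eye covariate (3,000 trials per setting, c = 0.7, r = 0.5) gave 88.4% unadjusted and 95.4% adjusted, with type I error 4.6% and 4.5%.
- Comfort, SD 2.5, Visits 2 and 3 averaged, between-visit correlation v = 0.5: k = √((1 + v)/2 − r²), giving 89.9/91.3/97.3%.

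**Missing baselines.** Let a share m be missing completely at random. If those subjects are dropped, the SE ratio to the unadjusted analysis is √((1 − r²)/(1 − m)). Adjustment then loses precision once m exceeds r²: 4%, 9% and 25% at r = 0.2, 0.3 and 0.5. With overall-mean imputation the ratio is √(1 − r²(1 − m)). For comfort, SD 2.5 and m = 0.05 (unadjusted 81.2%):

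| r | SE ratio: dropped / imputed | Power: dropped / imputed |
|---|---|---|
| 0.2 | 1.005 / 0.981 | 80.8% / 82.5% |
| 0.5 | 0.889 / 0.873 | 88.5% / 89.5% |

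A simulation of the r = 0.5 case (10,000 trials) gave 82.1% unadjusted, 88.8% dropped and 89.9% imputed, with type I error 4.9%, 5.0% and 4.9%.

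**The case against.** The planned model is legitimate: omitting a prognostic covariate is a choice about efficiency, and nothing in the documents promises baseline adjustment. That is correct, and it is why this is a recommendation and not an error of validity.

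The benefit may also be slight. Comfort, VA, wetting and deposits at Visit 1a are measured on habitual lenses, whereas follow-up is on a randomly assigned lens type. Sections 7.5.2 and 7.5.3 set wear times before the follow-up visits; section 7.4 sets none for Visit 1a. Eligibility restricts the spread of the slit lamp grades. All of this points to modest correlations or small SDs. By the same formula, unadjusted power is already about 99.5% at comfort SD 1.5 and about 99% at VA SD 0.08. These limits stand. They bound the gain, but they do not make adjustment harmful once missing baselines are handled.

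For VA, Visit 1b records acuity in the assigned study lens before the solution is issued, so it could be a better covariate for that endpoint. A covariate-by-visit term could also be added. Both are reasonable refinements and neither argues for leaving baseline out.

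Missing Visit 1a values should be rare, because the measurements precede the eligibility checklist, and the 5% share above is only illustrative. An imputation rule is still needed, since under the general exclusion rule each missing value would cost follow-up data.

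Naming the response and decision visits is a separate matter of specification. The precision argument does not depend on it.

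**Conclusion.** The point holds. None of the seven primary models uses the Visit 1a value, it is available before assignment for every endpoint, and no reading of the visit factor with a free interaction recovers the lost precision.

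The loss is one of efficiency only. Where starting power is 81-92%, adjustment adds about 1-2 percentage points at r = 0.2 and 5-9 points at r = 0.5. The gain matters mainly for comfort and VA if their SDs are large. It is small for the five 0-4 grades unless SDs are near 1, and small for any endpoint if r is low. Every figure depends on assumed SDs and correlations, because the documents give none. The change is worth making because it is nearly free, but the trial's validity does not depend on it. Confidence that the benefit is material is moderate.

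**What to change.** Amend section 10.2 as follows:

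1. Add the Visit 1a value of the same endpoint as a fixed covariate in each of the seven models, with Visits 2 and 3 as the only response visits. Use the per-eye value where the endpoint is recorded per eye, the film grade for deposits, and the sector-averaged grade for corneal staining. For comfort, use the same rating, or mean of ratings, that is analysed at follow-up.
2. Exempt this covariate from the rule that excludes missing data. Replace a missing Visit 1a value by the overall baseline mean with both arms pooled, so that no follow-up data are lost.
3. In the same sentence, name the visit at which the Test minus Control difference is judged.

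The cost is one degree of freedom per model, one imputation rule and one sentence on visits. No new data or visits are needed. If the correlation proves low, the gain is close to zero.

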A sterile, isotonic solution that contains hyaluronan, sulfobetaine, poloxamine, boric acid, sodium borate, edetate disodium and sodium chloride and preserved with a dual disinfection system: polyaminopropyl biguanide 0.00013% and polyquaternium 0.0001%.

This will be used with a rub and rinse step.

CONTACT LENSES: The following six lens types will be used to represent a cross-section of lenses in use: ACUVUE® 2, ACUVUE® VITA® (Johnson & Johnson Vision Care), Air OPTIX® (Alcon), Biofinity®, Clariti (CooperVision), PureVision® (Bausch & Lomb)

Approximately 33 subjects will be allocated to use each lens type: 22 using the test MPS product and 11 using the control product. Each site will use four lens types.

NO. OF SITES: Approx. 10 (3-5 UK and 5-6 US) sites. Each site will enroll approx. 20 subjects.

NO. OF SUBJECTS: Total approx. 200 subjects (400 eyes), approx. 20 subjects/site. The aim is for at least 180 subjects to complete the study; 30 in each lens group (20 using the test solution and 10 using the control solution).

	Test Group	Control Group	Total Subjects
Site 1 to 10	~14	~7	~20
Total	133	67	200

STUDY POPULATION:	Volunteer subjects will be currently adapted soft contact lens wearers (>1 month of lens wear), be at least 18 years of age with contact lens sphere power requirement in the range +4.00 to -8.00D and refractive astigmatism of less than or equal to 0.75D in each eye.
VARIABLES:	
Comfort (0-10)
 
Average wearing time (WT), comfortable WT (hrs.)
 
Visual acuity (Snellen/logMAR)
 
Slit lamp findings, including corneal edema, limbal and bulbar hyperemia, vascularization, palpebral hyperemia and roughness, corneal staining, conjunctival staining, etc. (0-4)
 
Lens surface wettability (0-4)
 
Lens surface deposits (0-4, no. of spots)
 
Adverse events

IN VITRO MEASUREMENTS:	Deposit analysis in dark field illumination using a modified version of the method of Lowther et al (ICLC 1991;18:219-26) on approx. 60 lenses.
VISITS/SCHEDULE:	
There will be four scheduled visits (visit 1a and 1b may be conducted on the same day):
 
Visit 1a: Baseline
 
Visit 1b: Lens issue
 
Visit 2: 1 week follow-up (7 days \pm3 days) – WT 1-3 hours
 
Visit 3: 1 month follow-up (30 days \pm4 days)

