3.2 Randomization

Subjects will be randomly assigned to use either the test or control solution. Two codes will be used for the test product and one code for the control so there are equal numbers of bottles of each code ('A', 'B' or 'C'). Subjects will also be randomly assigned to a lens type.

A random number generator (Microsoft Excel) will be used to determine the randomization of solutions and lens types. Each eligible subject will randomly be assigned to one of the lens care products and lens types using a blocking method and stratified by site. All sites will use both the test and control solutions. Each site will only use four of the six study lens types.

The randomization will be performed in stages. Firstly, the sites will be randomly assigned to four of the six study lens types. Secondly, subjects will be randomly allocated, by site, to one of the four lens types in blocks of four subjects. Thirdly, subjects within each site and lens type will be randomly allocated to one of the three solution codes (2 x Test, 1 x Control) in blocks of three subjects.

Subject ID numbers will be assigned consecutively to maintain randomization.

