5.3 Study Contact Lenses

Subjects will be randomly allocated to use one of six lens types (Table 2). Approximately 33 subjects will be allocated to use each lens type: approximately 22 using the test MPS product and 11 using the control product.

Each investigational site will use four of the six lens types (e.g. Types 1,2,3,4 or Types 1,2,5,6 or Types 3,4,5,6). Each site will utilise a stock of lenses so that, where possible, subjects may be dispensed lenses at the first visit. However, if the appropriate lenses are not immediately available, a second visit (Visit 1b) will be scheduled.

One of the lenses (Acuvue 2) is recommended for 2-weekly replacement. For these subjects, spare lenses will be issued during the Baseline visit with instructions for replacement.

In the event of lens loss or damage, replacement lens(es) will be issued at an unscheduled visit.

Table 2: Contact Lens Details

	Type 1	Type 2	Type 3	Type 4	Type 5	Type 6
Brand	ACUVUE® 2	PureVision®	Clariti	ACUVUE® VITA®	Air OPTIX®	Biofinity®
Manufacturer	Johnson & Johnson Vision Care	Bausch & Lomb	CooperVision	Johnson & Johnson Vision Care	Alcon	CooperVision
Material type	Conventional hydrogel	SH ionic, plasma oxidation surface treatment	SH non-ionic, not surface treated, high water	Silicone hydrogel (SH) non-ionic, not surface treated; contains PVP	SH non-ionic, surface modification by plasma polymerization	SH non-ionic, not surface treated; contains monomer n-vinyl pyrrolidone
Material	etafilcon A	balafilcon A	somofilcon A	senofilcon C	lotrafilcon B	comfilcon A
Water content	58%	36%	56%	41%	33%	48%
FDA Group	Group 4	Group 5A	Group 5B	Group 5Cr	Group 5Cm	Group 5C
Base curve / Diameter (mm)	8.30, 8.70 / 14.0	8.60 / 14.0	8.40 / 14.1	8.40 / 14.0	8.60 / 14.2	8.60 / 14.0
Replacement period	2-weekly	Monthly	Monthly	Monthly	Monthly	Monthly
Powers (D)	+4.00 to -8.00					

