7.5.3 Visit 3: 1-month Follow-up

The 1-month follow-up visit will be scheduled 4 weeks (30 ± 4 days) from the dispensing date. The subjects should wear the lenses for a minimum of 2 hours prior to the appointment. If the subject attends without lenses or with less than 2 hours of lens wear on that day and they are not having any problems with their lenses or the study solution, the visit should be rescheduled, if possible within the visit window.

The subject will be asked a small number of questions relating to the study care solution.

The same assessments will be followed as at the 1-week visit and will be recorded on the Follow-Up Visit eCRF. At the UK sites (if requested) worn lenses will be retrieved for return to Visioncare Research for *in vitro* analysis.

The kit-boxes containing any remaining study solution will be collected from the subjects. The Kit-box accountability log will be completed and the kit-boxes returned to Visioncare Research at the end of the study.

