Comparisons between the test and control solutions will be carried out using pairwise one-sided confidence intervals constructed for least-square mean differences (mean difference calculated as Test minus Control). Non-inferiority will be concluded if the lower confidence limit is greater than -0.5.

Analysis of deposits: Results will be analyzed using a linear mixed model including the experimental design factors: solution type, visit and their interaction will be included as fixed effect factors and site and subject as random effects.

Comparisons between the test and control solutions will be carried out using pairwise one-sided confidence intervals constructed for least-square mean differences (mean difference calculated as Test minus Control). Non-inferiority will be concluded if the upper confidence limit is less than +0.5.

Analysis of slit lamp findings: First the results will be averaged across each sector. Average results will be analyzed using a linear mixed model including the experimental design factors: solution type, visit and their interaction will be included as fixed effect factors and site and subject as random effects.

Comparisons between the test and control solutions will be carried out using pairwise one-sided confidence intervals constructed for least-square mean differences (mean difference calculated as Test minus Control). Non-inferiority will be concluded if the upper confidence limit is less than +0.5.

Additional analyses:

- Overall occurrence of slit lamp findings of Grade 2 or higher
- Overall occurrence of lens VA findings worse than 6/12 (20/40)
- Overall occurrence of clinically significant lens surface deposits (>Grade 1)
- Ocular adverse events.

Any deviations from the above analysis will be documented in the report.

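### Solution is randomised within lens type, but section 10.2 leaves lens type out of every primary model and names no by-lens result

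*Combined protocol and SAP*

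**What the plan says.** Section 3.2 allocates in stages: sites to four of the six lenses, subjects to lens type in blocks of four within site, and then "subjects within each site and lens type will be randomly allocated to one of the three solution codes", in blocks of three (two test, one control). Site and lens type therefore both stratify the allocation of solution.

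The lenses are a deliberate part of the design. The Synopsis says that "six lens types will be used to represent a cross-section of lenses in use", and sets a completer target for each: "30 in each lens group (20 using the test solution and 10 using the control solution". Section 1 describes the product as suitable for all soft lenses.

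Section 10.2 introduces each model as containing the factors of the experimental design, and then lists "solution type, visit and their interaction will be included as fixed effect factors and site and subject as random effects". The same list serves comfort, visual acuity, wettability, deposits and slit lamp findings, which cover the seven hypotheses of section 2.1. On summaries it says: "Descriptive statistics will be reported by solution type at baseline, dispensing, and each follow-up visit according to ISO 11980:2012". Three of the four additional analyses are overall occurrences, for example "Overall occurrence of slit lamp findings of Grade 2 or higher"; the fourth is ocular adverse events, with no stated breakdown.

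**The concern.** The analysis does not follow the randomisation. Stratifying by a factor that predicts outcome balances the arms and so reduces the true variability of the treatment difference. A model without that factor leaves its variance in the error term, and the reported standard error is then too large.

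The protocol itself gives a reason to expect lens effects, at least on deposits and wettability. Section 5.3 states: "One of the lenses (Acuvue 2) is recommended for 2-weekly replacement". Table 2 gives monthly replacement for the other five. The last visit falls on day 26–34 (section 7.5.3). With replacement every 14 days, an ACUVUE 2 lens is then at most 14 days old (12–14 days just before the day-28 change, 0–6 days after it). The other lenses are 26–34 days old unless replaced after loss or damage. Table 2 also shows different materials, water contents and FDA groups.

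A second matter is separate from precision. The hypotheses are pooled over lenses, so a solution effect confined to one lens material is averaged with five others. Pooling is the stated estimand and is not an error. But section 10.2 names no output in which such an effect would appear.

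**Working it through.** **The plan's own figures.** 180 completers / (1 − 0.10) = 200 enrolled. 200 × 2/3 = 133 test and 67 control. 200/6 = 33 per lens, split 22 and 11. Completers: 120 and 60 overall, 20 and 10 per lens. All agree with the Synopsis and sections 4.2 and 5.3. Section 10.1 states no power or SD, so there is no power calculation to reproduce, and every SD below is an assumption.

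**Precision: closed form.** If lens type explains a share R² of within-site variance and solution is perfectly balanced within lens, the standard error is inflated by 1/√(1 − R²) and the true one-sided error is 1 − Φ(1.645/√(1 − R²)).

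| Assumed R² | SE inflation | True error (nominal 5%) |
|---|---|---|
| 0.05 | 2.6% | 4.6% |
| 0.10 | 5.4% | 4.1% |
| 0.20 | 11.8% | 3.3% |
| 0.30 | 19.5% | 2.5% |

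This is an upper bound, because about five subjects per site-and-lens cell (20/4), allocated in blocks of three, are only partly balanced.

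**Precision: simulation of the section 3.2 design.** Ten sites of 20; the three example lens sets of section 5.3; lens blocks of four and solution blocks of three; 10% random drop-out; two visits with within-subject correlation 0.5; random site effect with SD 0.2 of the residual SD; one-sided 95% limit for the 1-month contrast. Eyes are averaged to one value per subject and visit. There were 12,000 runs per setting.

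Below, ratio is the between-lens SD divided by the residual SD. Standard errors are in residual-SD units.

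| Ratio | Model SE without lens | True SE | Excess | Error without lens | Error with lens |
|---|---|---|---|---|---|
| 0 | 0.158 | 0.158 | none | 5.1% | – |
| 0.3 | 0.164 | 0.159 | 3% | 4.4% | 4.7% |
| 0.5 | 0.173 | 0.161 | 7% | 3.8% | 4.9% |

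Power with no true difference, without against with lens type in the model:

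| Margin/SD | Example | Ratio 0.3 | Ratio 0.5 |
|---|---|---|---|
| 1.0 | 0.5-margin endpoint, SD 0.5 | about 100% v 100% | about 100% v 100% |
| 0.71 | 0.5-margin endpoint, SD 0.7 | 99.7% v 99.7% | 99.6% v 99.8% |
| 0.5 | comfort SD 2.0, or VA SD 0.10 | 92.6% v 93.4% | 90.5% v 93.4% |
| 0.4 | comfort SD 2.5, or VA SD 0.125 | 78.8% v 80.5% | 75.6% v 80.5% |

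A second, independent simulation at ratio 0.5 gave a model SE of 0.174 against 0.167, error 4.2%, and power 75.0% against 79.9% at margin/SD 0.4.

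**Dilution.** This needs no SD. Each lens holds about one-sixth of subjects, so a difference d confined to one lens gives an expected pooled difference of d/6. That equals the margin when d = 6 × 0.5 = 3.0 grades on a 0–4 scale, or 6 × 1.0 = 6.0 comfort points out of 10.

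As an illustration, take d = 1.0 grade and no other lens effect. The pooled pass probability is Φ((0.5 − d/6 − 1.645·SEm)/SEt), with SEm² = (sd² + 5d²/36)/120 + sd²/60 and SEt² = sd²/120 + sd²/60.

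- sd 0.5: (0.3333 − 1.645 × 0.0861)/0.0791 = 2.43, so 99%.
- sd 0.7: (0.3333 − 1.645 × 0.1158)/0.1107 = 1.29, so 90%.
- sd 0.9: (0.3333 − 1.645 × 0.1463)/0.1423 = 0.65, so 74%.

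With lens main effects at ratios 0.3–0.5 (3,000 runs each), the planned model passes 98%, 84–88% and 66–70% of the time. With lens type added, the figures are 99%, 89–90% and 73–74%. The covariate restores precision; it does not reveal the one-lens difference. For corneal staining, 1.0 grade means one grade averaged over all five sectors.

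**By-lens precision.** The one-sided 95% half-width is t(0.95, 28) × sd × √(1/20 + 1/10) = 1.701 × sd × 0.387: 0.33 at sd 0.5 and 0.46 at sd 0.7. With no true difference, one lens would clear a 0.5 margin about 81% and 56% of the time.

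**The case against.** The strongest reply is about weight. Omitting the covariate makes the test conservative, so it cannot add false non-inferiority claims, and only the sponsor bears the cost. That cost is 0.2 points of power or less for the five 0.5-margin endpoints at SD 0.5–0.7. The largest loss shown needs both a margin of 0.4 SD and a between-lens SD half the residual SD, and the documents establish neither. All of this stands.

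On dilution, the hypotheses are pooled. A 1.0-grade difference in one lens is a pooled difference of 0.167, well inside 0.5, so passing is the correct decision under the stated hypothesis. This also stands: the pass rates above are not error rates. What remains is that no named output would bring such a difference to light.

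The descriptive summaries follow ISO 11980:2012, which may call for by-lens tables. It cannot be consulted here, so the claim is limited to what section 10.2 names. Section 8.1 promises a tabulation of device-related adverse events, and section 8.3 records whether an event is attributed to lens or care product, but neither states a breakdown by lens worn.

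Lens age does not confound the comparison, because ACUVUE 2 users are in both arms; it matters only as a source of variance. Finally, the simulation's use of the 1-month contrast and of the example lens sets is an assumption, since section 10.2 names no decision visit and section 5.3 gives the sets only as examples. None of these points supplies a lens term or a by-lens result.

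**Conclusion.** The point holds and should be corrected, though it does not threaten validity. Lens type stratifies the allocation of solution and is absent from all the primary models, and section 10.2 names no by-lens output. Neither fact depends on an assumption.

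The size of the precision loss does. It is nil if lens type has no effect, negligible for the 0.5-margin endpoints at SD 0.5–0.7, and from about 1 to 5 points of power where the margin is 0.4–0.5 SD, which may apply to comfort and visual acuity. The six-fold dilution needs only equal lens groups; it is a property of the pooled estimand and becomes a gap because nothing by lens is reported beside it.

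**What to change.** In section 10.2:

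1. Add lens type as a fixed effect in the models for all seven primary hypotheses. This corrects the standard error; it does not address dilution.
2. Add a supportive model with a solution-by-lens-type term, and report the Test minus Control difference with its confidence limit for each lens. Label these results descriptive, not six non-inferiority tests.
3. Tabulate slit lamp findings of Grade 2 or higher, deposits and adverse events by solution and lens type.

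The change is to wording only. Lens type is already recorded on the Dispensing eCRF (section 7.5), and no further subjects are needed. The covariate uses five degrees of freedom. By-lens intervals will be wide at 20 against 10 completers, some lenses will miss a 0.5 margin by chance, and by-lens adverse event tables will be sparse. That is why these results should be descriptive and specified in advance.
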